2. INTRODUCTION

Medicines are the most common therapeutic intervention in healthcare, yet the efficacy and safety of many drugs show considerable inter-personal variation. Some patients are prescribed inefficacious medication, whereas others develop adverse drug reactions. This variation has a significant personal, clinical, and economic impact, leading to poorer individual and societal outcomes. Strategies are required to reduce this variability. One approach is to leverage knowledge of an individual's genetic information to support medicines optimisation, better informing medicine selection and dosing (pharmacogenomics).

Evidence-based guidelines to support pharmacogenetic-guided prescribing are available for many commonly prescribed medicines. Despite a good understanding of these medicine-gene relationships, clinical implementation in the UK is limited to a small number of medicines. This is typically carried out reactively, where single genes are analysed when a medication is considered.

Given the high population frequency of genetic variation which influences the efficacy and safety of medicines, an alternative approach to pharmacogenetic guided prescribing is pre-emptive panel testing. This involves testing individuals for many common pharmacogenetic variants at a set time, irrespective of the medicine they are prescribed. This information can then be integrated into a patient's medical records and used to inform prescription. Currently, there is limited evidence suggesting how such an approach would impact on prescribing behaviour in the UK.

The Implementing Pharmacogenomics to Improve Prescribing (IPTIP) trial is a cross-sectional study linking patient genotype with prescribing data to measure the clinical utility of preemptive pharmacogenetic panel testing. This will determine the potential clinical value of the approach, both in the primary and secondary care settings, and identify key cohorts where targeted testing might be most appropriate. Implemented effectively, pharmacogenetics has the potential to improve patient outcomes. The output from the IPTIP trial will inform the development of a local and national pharmacogenetic service.

3. BACKGROUND

3.1. What is the problem being addressed?

It is a well-recognised clinical phenomenon that patients display variation in their response to medicines.¹ Consider three patients in pain, all prescribed the same dose of codeine. The first responds appropriately, the second appears to receive no analgesic relief, whilst the third develops symptoms of opioid toxicity. Such variation in response and side-effects is a frequent and often frustrating feature of clinical practice.

Such variation is regularly attributed to the chosen dosing strategy, the accuracy of the initial diagnosis or individual factors, such as co-morbidities, polypharmacy or compliance.¹ There is evidence that response to a medicine is impacted by an individual's genetic make-up, a concept known as pharmacogenomics. Codeine requires activation to morphine by the hepatic cytochrome CYP2D6.² Common genetic variants in the *CYP2D6* gene impact the function of the CYP2D6 enzyme. Considering the above scenario, the second patient, like 10% of the population, may be a poor CYP2D6 metaboliser, meaning they fail to effectively convert codeine into morphine. Meanwhile, the third patient may represent approximately 2% of individuals who are ultra-rapid CYP2D6 metabolisers, in danger of producing high morphine levels, leading to toxicity.

Codeine is just one example of a medicine with evidence for informing prescribing based on genotype. Good evidence exists for many other commonly prescribed medicines including clopidogrel, tricyclic antidepressants, proton-pump inhibitors (PPIs), statins and anticoagulants.^{3–7} Despite this, clinical implementation, especially in the UK, is limited to a few specific indications, namely azathioprine, abacavir and fluoropyrimidine chemotherapy agents.^{8–10} Current implementation typically involves a "reactive" testing strategy, where patients are tested for genetic variation relating to the medicine they are being prescribed at that moment in time. Many argue

that a prospective testing approach, using gene-panels, is a preferable model. 11-13

Proponents cite the high prevalence of clinically relevant pharmacogenetic variants in the population and the widespread use of medicines for which pharmacogenetic dosing-guidelines exist.

There is evidence to support genotype-guided prescribing for a range of medicines and the cost of genetic sequencing has fallen to allow use in clinical practice. Despite this, there are remaining barriers to prospective pharmacogenetic testing, as evidenced by the lack of clinical implementation across the UK. These barriers were recently discussed as part of a policy discussion, and the contributors specifically highlighted a paucity of evidence around real-world clinical utility. The IPTIP trial aims to address this, by determining the clinical utility of pharmacogenetic data using both historical and contemporaneous prescribing data.

In this proposal, clinical utility refers to the concept that an individual would have their prescription altered based on their genotype. A cross-sectional survey of US veterans found 99% carried an actionable pharmacogenetic variant. However, many of these variants were related to the metabolism of medications that the patient is not prescribed; therefore, clinical utility in those patients is low. Defining the clinical utility of pharmacogenetics on a more granular level is critical when considering implementation strategies. If overall clinical utility is high, then a pre-emptive panel approach is likely to be a practical approach, otherwise, more targeted testing strategies may be appropriate. The integration of pharmacogenetics within clinical practice represents a complex intervention, as defined by the Medical Research Council, and causal assumptions which underpin any intervention should be well characterised before implementation. By linking genotype and detailed prescribing data, the IPTIP trial will define clinical utility and identify cohorts where pharmacogenetic testing is of particular benefit.

3.2. Why is this Research Important?

Medicines are the most common intervention in healthcare. Almost half of all UK adults regularly take prescription medicines. ^{18,19} The NHS's annual budget for medicines is approximately £17.4 billion per year, with over 1.1 billion items prescribed. ^{11,20} Given this, even small improvements in effectiveness and safety could have significant health benefits at the individual and population level. As such, The Royal Pharmaceutical Society promotes medicines optimisation, which aims to ensure that the patients get the right medicine, at the right dose, at the right time. ¹⁸

Effective medicines optimisation is important on both an individual and a societal level.

Adverse drug reactions (ADRs) account for 6.5% of hospital admissions and 14.7% of extended hospital stays. This equates to approximately 8000 hospital beds occupied at any one time, estimated to cost the NHS £1.6 billion per year. There is good evidence, for multiple gene-medicine pairs, that pharmacogenetics could be used to improve efficacy and to reduce the rate of ADRs. The IPTIP trial aims to investigate the clinical utility of pharmacogenetics which will contribute to improved strategies for medicines optimisation, increasing efficacy whilst reducing ADRs.

A 2018 analysis of a primary and secondary care prescribing found that PPIs, statins, antiplatelets and antidepressants were some of the most commonly prescribed items.²³ All of these classes of medicine have guidelines for genotype-guided prescribing. Polypharmacy (concurrent prescribing of medication) is common. There is evidence to suggest that if patients are prescribed a medicine with pharmacogenetic guidance, they are highly likely to also be prescribed other medicines with similar guidelines.²⁴ As such, panel testing could be a powerful approach to optimise an individual's whole prescription, rather than a single medicine. In addition, once generated, these data will remain valuable throughout an individual's life.

Integrating pharmacogenetics into clinical practice has the potential to lead to improved effectiveness and reduce ADRs, therefore optimising patient outcomes whilst using NHS resources effectively. To achieve effective integration, it is necessary to measure the clinical utility of pharmacogenetics, and design intelligent implementation strategies reflective stakeholder preferences.

There is a significant unmet need to better understand the clinical utility of pharmacogenomics. Recognising this, the IPTIP trial has been fully funded by the National Institute for Health Research (NIHR) based on the protocol below, which was reviewed as part of the application process. The award for the study forms part of a Doctoral Research Fellowship (DRF) award for [name]. In summary, the results from this work will have broad applicability and will contribute to the design of services, on both local and national levels, which will improve outcomes for patients across multiple clinical specialities.

4. STUDY OBJECTIVES

4.1. Primary Question/Objective:

If a pre-emptive pharmacogenetic test were implemented, what proportion of patients would have their prescriptions adjusted based on the results?

4.2. Secondary Question/Objective:

Are there specific groups of patients in whom pre-emptive screening would be of heightened value?

5. STUDY DESIGN & PROTOCOL

5.1. Participants

A minimum of 646 participants will be recruited across two groups. Participants will be recruited from an outpatient (IPTIP-O) and inpatient (IPTIP-I) setting at the Manchester University NHS Foundation Trust (MFT). As the largest acute hospital trust in the UK, recruitment will access a population from diverse ethnic and socio-economic backgrounds.

- IPTIP-I: Patients admitted to the Manchester Royal Infirmary (MRI) will be recruited. The MRI is large tertiary referral centre with over 750 medical and surgical beds and the Acute Medical Unit (AMU) has a throughput of approximately 200 patients per week.
- IPTIP-O: Patients and their relatives who have an outpatient appointment with the
 Manchester Centre for Genomic Medicine (MCGM) or have previously had an outpatients
 appointment and are still in follow up with the clinical genetics service, will be eligible for
 recruitment. The MCGM serves a population of 5.7 million and there are over 10,000
 appointments each year.

5.2. Study Intervention and/or Procedures

For the Inpatient arm (IPTIP-I), eligible patients admitted to the Manchester Royal Infirmary will be provided with a written Patient Information Leaflet (PIL) after admission to the ward. Participants will be provided as much time as they wish to consider participation before written informed consent is taken. Those meeting eligibility criteria will be approached by the study team, and consent will be taken whilst on the ward. Consent will be taken by a delegated member of the research team or clinical team involved in the patient's care.

Adults who have an appointment with the MCGM will be identified by the reviewing clinician. For the outpatient arm (IPTIP-O), participants will be given a patient information leaflet (PIL) and a clinic room will be reserved for recruitment where the patient is seen face-to-face. Where the patient has been reviewed virtually, the PIL can be sent via post or e-mail. For IPTIP-O recruitment, consent will be taken at the time of the appointment where the patient is attending face to face, or via the completion and return of a consent form via the post where the patient has had a virtual appointment. The consent form will be posted with a freepost envelope included to return.

For the IPTIP-I arm, all consent will be taken or over during the participant's admission (IPTIP-I).

5.3. End of Study

The end of study will be defined as the date of the last participant recruited plus 6 months for data analysis. Participants will consent for their prescribing data to be made accessible for 5 years following this defined end of study, to allow time to monitor future prescribing practice.

6. STUDY PARTICIPANTS

6.1. Inclusion Criteria:

- Participants must be admitted to the Manchester University NHS Foundation Trust or have attended an outpatient appointment, as a patient or relative/carer/partner, at the Manchester University NHS Foundation Trust
- Participants must have capacity to independently consent
- Patients must be over the age of 18 years.

6.2. Exclusion Criteria:

- Patients unable to independently consent
- Patients under the age of 18

6.3. Recruitment:

As outlined above (section 5.2), recruitment will take place in 2 locations at a single site. The recruitment approach will differ slightly between IPTIP-I and IPTIP-O. All patients will be asked to consent to the following:

- Blood sampling for DNA extraction or saliva sampling for DNA extraction (if
 difficulties in obtaining a blood sample as first choice) or access to stored DNA where a
 sample has already been taken for a previous clinical indication.
- 2. Access to inpatient prescribing data
- 3. DNA analysis related to pharmacogenetics
- 4. Sharing of identifiable data with Graphnet CareCentric, who operate the Greater Manchester Care Record (GMCR), to allow data retrieval from primary care records.
- 5. Access to historical and future healthcare data via the Greater Manchester Care Record (GMCR)
- 6. Transfer from the Greater Manchester Care Record (GMCR) into the NHS GM Analytics and Data Science Platform (ADSP) for analysis and storage for a maximum of 5 years after the end of the IPTIP study.
- 7. Where access to the GMCR is not possible, because the patient is not registered with a General Practitioner in Greater Manchester, permission will be sought to access prescribing history via the Summary Care Record (SCR).
- 8. Sharing of anonymized data and patient samples for ethically approved research.
- 9. Patients will have the **option** of consenting for a buccal sample (cheek swab) to be taken alongside the blood or saliva sample. This will be used to assess whether it is possible to test for the pharmacogenetic variants more quickly using a non-invasive sample.

6.3.1. IPTIP-I Recruitment

The acute medical unit (AMU) at the Manchester University NHS Foundation Trust (MFT) is 48 bedded unit. This represents one of several acute wards at the Manchester Royal Infirmary. Recruitment will take place in one of three wards (AMU, Manchester Vascular Centre, and the Acute Care Unit) — ensuring a diverse cohort of patients are recruited. Each day during the recruitment period a randomised list of the beds across the three wards will be generated, and the patients will be approached in this order, minimising sampling bias to avoid the sample being skewed towards those more amenable to recruitment such as the young or English speaking. This approach will endeavor to ensure that individuals across all age groups, both sexes and all ethnicities are included. Every month, average participant demographics will be compared against existing control data to ensure a representative sample of the inpatient population is being recruited. The patients will be approached by the direct clinical or research team (CRN research support and sub-investigators), the study will be discussed and a PIL will be provided. Thereafter, if the patients wish to enrol, a

consent form will be signed, blood or saliva (+/- buccal) samples for DNA extraction will be taken and the initial recruitment proforma will be completed, generating a unique study ID.

6.3.2. IPTIP-O Recruitment

The MCGM serves a population of 5.7 million and there are over 10,000 appointments each year. Participants will be recruited from the MCGM outpatient department, a dedicated unit where a clinic room will be reserved for IPTIP recruitment. Anyone attending the MCGM, including the consultee and their relatives, carers or partner, will be eligible for recruitment, within the scope of the exclusion criteria as described above (Sections 6.1 and 6.2). Participants will be identified by the reviewing clinician in clinic, or by writing to patients who have previously been seen in the department and are still under follow up with the clinical genetics service. As a result of the COVID-19 pandemic, there is an approximately 50:50 split between face-to-face and virtual clinic appointments. As such, we propose both face-to-face and virtual consenting processes, to facilitate recruitment and ensure those who cannot travel as easily are not prevented from participating. For face-to-face appointments, interested individuals will be invited for a discussion with the research team in the reserved consultation room and the study will be discussed, during which a PIL will be provided. If patient's wish to have more time to consider the study, they will be offered a follow up telephone or videocall. Where patients wish to enroll during clinic, a consent form will be signed, blood/saliva samples for DNA extraction will be taken (if a stored sample not already available) and the initial recruitment proforma will be completed, generating a unique study ID.

For virtual appointments or where patients indicated they would like more time to consider the trial, a telephone or video call (NHS Attend Anywhere or Microsoft Teams) will be arranged with the research team to discuss the study. Following this phone call if the patient is happy to receive information about the study, an information sheet and consent form will be posted to the participant with a pre-addressed return envelope. A short data collection form will be included with the consent form for patients to complete. This will allow accurate collection of demographic and drug allergy information, which would usually be completed as part of the initial recruitment proforma, if the patient was seen in a face to face clinic. If the patient wishes to participate, then they can return the completed consent form and data collection sheet in the pre-addressed return envelope. The contact details for the research team are on the patient information sheet should the patient wish to discuss the study with a member of the team after reading the patient information

sheet. If a DNA sample is already available then this will be accessed for the study, otherwise an appointment will be made for the patient to have their bloods taken for DNA extraction or a saliva sample will be sent in the post for completion and return. Where patients are contacted by letter to inform them about the trial, they will be offered a virtual consultation or a face to face appointment at their convenience.

If a patient has been sent the study information and has not returned a completed consent form after one month, then the research team may make contact with the patient to see if they are still interested in participating in the study and re-send the study information if required.

Each month, average participant demographics will be compared against existing control data to ensure a representative sample of the population attending the MCGM is being recruited. This data will then be fed back to the recruiting clinicians facilitating more tailored recruitment. Information regarding the trial will be placed on the North West Genomic Medicine Service Alliance (GMSA) website. This will be patient facing material (Appendix 2) which will provide information on the study and advise how interested participants can become involved.

6.4. Participants who withdraw consent:

Participants can withdraw consent at any time without giving any reason, as participation in the research is voluntary, without their care or legal rights being affected. Participants who withdraw their consent to be part of the study will have their data removed from the final analysis pipeline and their DNA sample will be destroyed. This will be made possible by de-anonymizing the final dataset via the secure study key (Section 8.3).

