7. OUTCOME MEASURES

The Primary outcome is the proportion of patients with a genotype related to a medicine they are currently, or have previously been, prescribed. Genotype-phenotype relationships will be assigned where there is high level PharmGKB evidence for clinical actionability (Levels 1A or 1B). Rates for the whole cohort will be presented but will be split by recruiting site and by age. These measures will be used to quantify the potential clinical utility of pre-emptive PGx testing in different settings, directly informing policy decisions around the implementation of PGx nationally.

In addition to the primary outcome, baseline characteristics will be presented. Medicine exposure by British National Formulary (BNF) class will be presented with sub-analysis by age group, sex, and the presence of recorded co-morbidities. Analysis will be presented for the whole cohort, and separately for inpatient and outpatient arms.

Genotype and metaboliser frequencies, derived using CPIC guidelines, will be presented for the whole cohort. These frequencies will then be analysed by age, sex, and ethnicity. Analysis will be presented for the whole cohort, and separately for inpatient and outpatient arms. Statistical differences in genotype based on demography, or recruiting site, will be tested via ANOVA or independent t-test. Genotype frequencies will be compared against an independent control cohort, generated as part of an ongoing trial, genotyping 1500 patients from the TARDIS Trial.²⁵ This will allow for comparison as to whether the dataset generated in this fellowship is consistent with others around the country, so clarifying generalisability.

Finally, the predictive value of patient variables, such age, co-morbid status, or ethnicity, for exposure to medicines where pharmacogenetic guidelines exist will be determined. This will be used to assess whether these variables, either in isolation or in combination, could be used to define a targeted screening approach for pharmacogenetics.

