9. STATISTICAL CONSIDERATIONS

9.1. Statistical Analysis

A Chi Square Test of Independence will be applied to assess whether the prevalence of actionable genotypes is the same in the IPTIP cohort as in existing control datasets (ie. TARDIS and Vanderbilt datasets). ²⁴ The criterion for an actionable variant is as previously detailed (Section 7.0). The primary outcome measure between the IPTIP-I and IPTIP-O cohorts will be compared using the same statistical approach. Statistical differences in genotype based on demography, or recruiting site, will be tested via ANOVA or independent t-test. Logistic regression analysis will be used to determine the predictive value of patient variables, such age, co-morbid status, or ethnicity, for exposure medicines where pharmacogenetic guidelines exist. Statistical support will be provided throughout the trial by an independent trial statistician, [name].

9.2. Sample Size:

Sample Size: Determined based on the primary outcome and calculated with assistance from the NIHR Research Design Service and an independent statistician, [name]. Sample size is calculated using the formula $n=Z^2xPx(1-P)/e^2$ where z is value from standard normal distribution corresponding to desired confidence level (Z=1.96 for 95% CI), P is expected true proportion, e is desired precision.

For the inpatient arm, a previous estimate from Vanderbilt, USA, suggests that 40% of patients had a genetic variant related to a medication that they were prescribed. Given the diversity of the population presenting to MFT and the relative over-medicalisation of healthcare in the USA, a lower prevalence of 0.3 will be chosen to represent P which, with a desired precision of 0.05 and a CI of 95%. This results in a required sample size of **323**.

For the outpatient arm, feasibility trials in Vanderbilt, USA, and the Netherlands suggest that approximately 30% of patients have a genetic variant which would impact prescribing of a medication they were actually prescribed.^{26,27} Therefore, a P of 0.3 will again be used, assuming the same precision and CI as above, generating a required sample size of **323**.

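### Relatives may co-enrol in IPTIP-O, yet the sample size and named tests assume independent participants and no family identifier is listed, so the ±5-point precision is not assured

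*Protocol*

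**What the plan says.** Three places in the protocol admit relatives to the outpatient arm.

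- Section 5.1 describes the arm as "Patients and their relatives who have an outpatient appointment with the" genomic medicine centre.
- Section 6.1 accepts people who "have attended an outpatient appointment, as a patient or relative/carer/partner".
- Section 6.3.2 states: "Anyone attending the MCGM, including the consultee and their relatives, carers or partner, will be eligible for recruitment".

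Sections 6.1, 6.2 and 6.3.2 set no limit on the number of participants from one family.

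The outcome in Section 7 has a genetic component: "The Primary outcome is the proportion of patients with a genotype related to a medicine they are currently, or have previously been, prescribed". The same section plans genotype and metaboliser frequencies for the whole cohort and for each arm.

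Section 9.2 uses n = Z²P(1−P)/e² for each arm. For outpatients it says: "Therefore, a P of 0.3 will again be used, assuming the same precision and CI as above". This gives 323, with no design effect. Section 9.1 states: "A Chi Square Test of Independence will be applied to assess whether the prevalence of actionable genotypes is the same" in IPTIP as in the control datasets. It uses the same test for inpatients against outpatients, and ANOVA or t-tests for genotype differences by demography or site.

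The recruitment fields in Section 8.1 and the contents of the final dataset in Section 8.3 include no family identifier and no marker for who was the index patient.

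**The concern.** First-degree relatives share genotype, so two members of one family carry less information than two unrelated people. The sample-size formula and every comparison named in Section 9.1 treat participants as independent. If relatives enrol together and their outcomes are positively correlated, three things follow. The true uncertainty of the IPTIP-O rate exceeds the planned ±5 points. An interval calculated as if participants were independent is too narrow. Tests of IPTIP-O against IPTIP-I, and of IPTIP against the controls, reject too often. Without a recorded family link, the analysis dataset offers no direct means of correcting this, whatever the SAP specifies.

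**Working it through.** **Inputs from the protocol.** Z = 1.96, P = 0.3, e = 0.05 and n = 323 per arm (Section 9.2); minimum total 646 (Section 5.1); 1500 TARDIS controls (Section 7).

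**Assumptions, because the protocol gives none.** Family share f, family size m and within-family ICC. Only IPTIP-O is inflated.

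**Step 1: the plan's figure.** 1.96² × 0.3 × 0.7 / 0.05² = 322.69, rounded up to 323; 2 × 323 = 646. The half-width at 323 is 1.96 × √(0.21/323) = 4.998 points. The target fails once the design effect exceeds 323/322.69 ≈ 1.001.

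**Step 2: with families.**
- Design effect: DE = 1 + f(m−1)ICC.
- Half-width: 1.96 × √(0.21 × DE/323).
- n needed for ±5 points: 322.69 × DE, rounded up.
- Coverage of a naive 95% interval: 2Φ(1.96/√DE) − 1.
- Error of a nominal 5% test: 2[1 − Φ(1.96/√V)].
- Between the arms, V = (1 + DE)/2.
- Against TARDIS, V = [((1 + DE)/2)/646 + 1/1500] / [1/646 + 1/1500].

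Results for pairs (m = 2):

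| f | ICC | DE | n for ±5 | Half-width (points) | Coverage | Error, I vs O | Error, vs TARDIS |
|---|---|---|---|---|---|---|---|
| 20% | 0.1 | 1.02 | 330 | 5.05 | 94.8% | 5.1% | 5.1% |
| 30% | 0.2 | 1.06 | 343 | 5.15 | 94.3% | 5.3% | 5.2% |
| 50% | 0.3 | 1.15 | 372 | 5.36 | 93.2% | 5.9% | 5.6% |
| 100% | 0.5 | 1.50 | 485 | 6.12 | 89.0% | 8.0% | 7.1% |

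**Step 3: which ICC is plausible.** Take carrier status at one locus under a dominant model, with non-risk allele frequency p. The parent–offspring correlation is (p³ − p⁴)/[p²(1 − p²)] = p/(1 + p). For siblings, p³ in the numerator is replaced by ¼p⁴ + ½p³ + ¼p². For assumed risk-allele frequencies of 0.05 to 0.30, first-degree correlations run from 0.41 to 0.49. A value near 0.5 therefore suits single-gene frequencies.

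The primary outcome also requires exposure to the matching medicine. For one gene, with exposure independent between relatives, ICC = exposure × genotype correlation × (1 − genotype prevalence) / (1 − P). With an assumed exposure of 0.5, correlation of 0.45 and prevalence of 0.6 (so P = 0.3), this is 0.5 × 0.45 × 0.4/0.7 ≈ 0.13. With half the arm in pairs, DE ≈ 1.06 and the half-width is about 5.2 points. The last row of the table is thus an extreme bound for the primary outcome.

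**The case against.** The strongest reply is that clustering is possible but not shown. Relatives are eligible, but the protocol does not say that they enrol alongside an index patient. Its recruitment routes mostly address individuals: identification by the clinician, letters to patients in follow-up, and posted consent for virtual appointments, which make up about half of the total. Carers and partners are not normally blood relatives. The total of 646 is a minimum, so recruiting beyond it could absorb a small design effect. IPTIP-I is untouched by this route. No interval method for the analysis is fixed, and the SAP, which is not shown, may address relatedness. All of this stands, and it limits the size of the problem.

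It does not remove the problem. The eligibility rule, the sizing formula, the named tests and the listed data fields are all fixed in the protocol, and an SAP can cluster by family only if family membership is recorded.

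A reader might go further and infer that the omission can never be repaired. The documents do not support that. Section 8.1 records name, date of birth and NHS number, and Section 8.3 keeps the re-identification key for five years after study end. Later linkage would be difficult but not impossible.

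A reader might also infer that accompanying persons invalidate the outpatient denominator, because Section 7 speaks of patients. But they are explicitly eligible, and Section 6.3.2 checks representativeness against everyone attending the centre. A flag for them is useful but secondary.

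**Conclusion.** The point holds as a gap in the plan: the ±5-point precision for IPTIP-O is not assured if relatives co-enrol, and the independence-based comparisons then err in the anti-conservative direction. Under the moderate assumptions the cost is about 0.05 to 0.4 points of half-width and 0.1 to 0.9 points of test error. The figures rest on assumed family shares and correlations, so no single corrected sample size follows from the protocol.

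It would be tempting to conclude that the stated precision has been lost or that the tests are seriously invalid. That would need nearly the whole arm to enrol in families with a correlation near 0.5. The protocol gives no family share, and such a correlation fits single-gene frequencies better than the primary outcome.

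**What to change.** 1. Add a family ID and an index/accompanying flag to the recruitment proforma (Section 8.1), and carry both into the pseudonymised dataset (Section 8.3).
2. In Section 9.1, specify family-clustered inference (GEE or Rao–Scott) for the IPTIP-O rate, the genotype frequencies and every comparison that includes IPTIP-O.
3. Use one randomly chosen member per family as a sensitivity analysis only, because it discards data. With half the arm in pairs it leaves about 242 people (323 × 0.75), and the half-width at P = 0.3 is 1.96 × √(0.21/242) ≈ 5.8 points.
4. In Section 9.2, restate the IPTIP-O precision as ±5 points under independence and slightly wider under a stated design effect.

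The cost is two fields, a few lines of text and slightly wider intervals. Clustered inference reports the uncertainty correctly but does not restore ±5 points. If that target must hold, the moderate scenarios need 330 to 372 outpatients, which is 7 to 49 more than planned.
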